### **3.5.1 Procedures for Participants Meeting Failure Criteria at a Study Visit **PRIOR** to the 36-month Primary Outcome Visit**

All participants who meet failure criteria **PRIOR** to the 36-month Primary Outcome Visit will undergo the following **additional** testing in the order specified below (1-5) at the visit when the failure criterion is met:

1. Random Dot Stereo Butterfly test (**masked**): tested in OFFICE spectacles at 33 cm.\*
2. Preschool Worth 4-Shape test (**masked**): tested in OFFICE spectacles at 33 cm.\*
3. Distance Randot Stereotest (**masked**): tested through **TOP** of HOME spectacles at 3 meters (with bottom half of lenses taped). (See *ETS3 Procedures Manual* for taping instructions)
4. Randot Preschool Stereoacuity Test (**masked**): tested through **TOP** of HOME spectacles at 33 cm (with bottom half of lenses taped) (See *ETS3 Procedures Manual*)\*
5. Cycloplegic Refraction (after the testing above is completed)

- 668     • The cycloplegic refraction must be performed 30 to 45 minutes following at least  
669       one application of cyclopentolate 1%.
- 670     • If the cycloplegic refraction reveals that the spectacles no longer meet the spectacle  
671       tolerance criteria according to section 3.12, the spectacle correction must be  
672       updated (both HOME and OFFICE spectacles).

673       \*Test distance for near stereoacuity and other binocular testing is 33 cm rather than 40 cm because of the focal  
674       length of the +3.00 D add.

675       If based on the cycloplegic refraction performed at this visit:

- 676       • The spectacle correction IS within tolerance (section 3.12) and does not need to be  
677       updated:
- 678           1. Failure is CONFIRMED at this visit.
  - 679           2. The participant should be prescribed BFLs (if in the SVL group) or continued in  
680           BFLs (if in the BFL group) (section 2.8)
  - 681           3. The participant should return in 2 months (window: 4 to 12 weeks) for their Post-  
682           failure Secondary Outcome Visit (section 3.7).
- 683
- 684       • The spectacle correction is NOT within tolerance (section 3.12) and needs to be updated:
- 685           1. Failure is NOT CONFIRMED at this visit.
  - 686           2. The participant should be prescribed new spectacles (according to the criteria in  
687           section 2.8) consistent with the participant's randomized group assignment to SVL  
688           or BFL spectacles.
  - 689           3. The participant will return for a Failure Confirmation Visit (section 3.6) in 2  
690           months (window: 4 to 12 weeks).

### 691       **3.5.2 Procedures for Participants Meeting Failure Criteria AT the 36-month Primary 692           Outcome Visit**

693       All participants who meet failure criteria AT the 36-month visit must have a cycloplegic  
694       refraction at the end of this study visit (after eye alignment, stereoacuity, and other binocular  
695       function testing, etc.):

- 696       • The cycloplegic refraction must be performed 30 to 45 minutes following at least  
697       one application of cyclopentolate 1%.
- 698       • If cycloplegic refraction reveals that the spectacles are no longer within the  
699       spectacle tolerance criteria according to section 3.12, then both HOME and  
700       OFFICE spectacle corrections must be updated.

701

702       **NOTE:** All eye alignment, stereoacuity, and other binocular function testing must  
703       already have been completed as part of the 36-month Primary Outcome visit (for all  
704       participants) before instilling cyclopentolate drops.

705

706       If the spectacle correction IS within tolerance (section 3.12) and does not need to be updated:

- 707           1. Failure is CONFIRMED at this 36-month visit.
- 708           2. SVL group participants should be prescribed BFLs and BFL group participants continued  
709           in BFLs (section 3.4.1)
- 710           3. Both groups should return in 2 months (window: 4 to 12 weeks) for their 38-month  
711           Secondary Outcome Visit (section 3.8).

- 712  
713 If the spectacle correction is NOT within tolerance (section 3.12) and needs to be updated:  
714 1. Failure is NOT CONFIRMED at this 36-month visit.  
715 2. Participants should be prescribed new spectacles (according to the criteria in section 2.8)  
716 consistent with their randomized group assignment.  
717 3. Participants should return for a Failure Confirmation Visit in 2 months (window: 4 weeks  
718 to 12 weeks).  
719 4. Regardless of whether study failure criteria are confirmed or not confirmed at the Failure  
720 Confirmation Visit, all SVL participants will be prescribed BFLs and all BFL participants  
721 will continue with BFL wear (section 3.4.1).  
722 5. Both groups return in 2 months (window: 4 to 12 weeks) following the Failure  
723 Confirmation Visit for their 38-month Secondary Outcome Visit. In this specific  
724 situation, the 38-month Secondary Outcome Visit will be scheduled at 40 months after  
725 randomization (section 3.8).

726 **3.6 Failure Confirmation Visit**

727 Failure Confirmation Visits occur 2 months (window: 4 to 12 weeks) after suspected failures that  
728 occurred for participants who were found to need a change in spectacles at that time. The  
729 purpose of the Failure Confirmation Visit is to determine whether failure criteria are met after  
730 the participant has been wearing the updated randomized treatment spectacles. Note that meeting  
731 *any* failure criteria in updated spectacles will be considered a CONFIRMED failure. It is not  
732 required that the participant fail the same criterion that was initially failed before the spectacles  
733 were updated (e.g., could have failed distance motor criterion initially but now fails near stereo  
734 criterion; this is still failure).

735 **NOTE:** The Failure Confirmation Visit (if required) is not allowed to be missed regardless of  
736 timing. If the timing of the Failure Confirmation Visit overlaps with a subsequent follow-up  
737 visit, the Failure Confirmation Visit must be completed *in lieu of* the follow-up visit (or  
738 *before* the 38-month visit). Regardless of whether any regularly scheduled follow-up visits  
739 have been missed, the Failure Confirmation Visit must be completed when the participant  
740 returns at the next study visit.

741 All testing in section 3.4 (same as 36-month Primary Outcome Visit) must be repeated at the  
742 Failure Confirmation Visit, with participants wearing their HOME spectacles or OFFICE  
743 spectacles (or appropriate trial frames) as specified.

- 744 • If failure criteria are NOT CONFIRMED at a Failure Confirmation Visit occurring  
745 before the 36-month visit, no changes are made to treatment and the participant  
746 continues with the next scheduled follow-up visit for which the participant is not  
747 currently in the window, regardless of how soon.
- 748  
749 • If failure criteria are NOT CONFIRMED at a Failure Confirmation Visit occurring after  
750 the 36-month Primary Outcome Visit, participants will:  
751     ○ Be prescribed BFLs (if in SVL group) or continued in BFLs (if in the BFL group)  
752         (section 3.4.1)  
753     ○ Return in 2 months (window: 4 to 12 weeks) for their 38-month Secondary  
754         Outcome Visit (section 3.8).

- 756     • If failure criteria are CONFIRMED at **ANY** Failure Confirmation Visit (regardless of  
757        timing), participants will:  
758        ○ Be prescribed BFLs if in the SVL group or continued in BFLs if in the BFL group  
759            (section 3.4.1)  
760        ○ Return in 2 months (window: 4 to 12 weeks) for their:  
761            • Post-failure Secondary Outcome Visit (section 3.7) if failure occurred prior to  
762              the 36-month Primary Outcome Visit or  
763            • 38-month Secondary Outcome Visit if failure occurred at the 36-month  
764              Primary Outcome Visit (section 3.8).

765     **3.7 Post-failure Secondary Outcome Visit (After Confirmed Failure)**

766     Post-failure Secondary Outcome Visits occur 2 months (window: 4 to 12 weeks) after a  
767     CONFIRMED failure at either a protocol-specified visit or a Failure Confirmation Visit. All  
768     testing procedures completed at the 38-month Secondary Outcome Visit (section 3.8) will be  
769     completed at this Post-failure Secondary Outcome Visit.

770     After a Post-failure Secondary Outcome Visit is completed:

- 771        • Further treatment is at investigator discretion (including whether to continue BFL or  
772            SVL spectacles).

773     **3.7.1 Treatment After the Post-failure Secondary Outcome Visit**

774     Participants with confirmed failure status (sections 3.5 and 3.6) who have completed a Post-  
775     failure Secondary Outcome Visit prior to 36 months may be prescribed treatment at investigator  
776     discretion. Note that office spectacles will no longer be prescribed.

777     **3.7.2 Follow-up After the Post-failure Secondary Outcome Visit**

778     Participants with confirmed failure status (sections 3.5 and 3.6) who have completed a Post-  
779     failure Secondary Outcome Visit prior to 36 months will return for follow-up at 12 months and  
780     24 months (with reduced testing as described below), and for the 38-month Secondary Outcome  
781     Visit (as described in section 3.8); all other study visits will be skipped.

782     At the 12- and 24-month visits, these participants will undergo the following (reduced) testing  
783     while wearing their habitual correction:

- 785        1. Monocular Visual Acuity Testing: Distance VA will be measured (right eye first) with the  
786            participant wearing habitual correction and without cycloplegia, using the same test method  
787            used at enrollment.
  - 788            • ATS-HOTV; e-ETDRS; OR crowded single-optotype or single-line HOTV, LEA  
789              SYMBOLS, or Snellen letters (Allen pictures and Tumbling E optotypes are NOT  
790              allowed)
  - 791            • NOTE: VA testing may be performed at the end of the visit.
- 792        2. Randot Preschool Stereoacuity Test with habitual correction
  - 793            • Tested in habitual correction at 33 cm (see *ETS3 Procedures Manual*)\*
- 794        3. Ocular Alignment Testing – cover/uncover test, SPCT, and PACT:
  - 795            • Wearing habitual correction at both distance (3 m) and near (33 cm) (see *ETS3*  
796              *Procedures Manual*)\*
- 797        4. Cycloplegic Refraction (required only if not completed within the past 12 months):

- 798     • The cycloplegic refraction must be performed 30 to 45 minutes following at least one  
799       application of cyclopentolate 1%.  
800       If the cycloplegic refraction reveals uncorrected refractive error, spectacle changes may  
801       be prescribed at investigator discretion.

802     **3.8 38-month Secondary Outcome Visit**

803     All participants will complete a 38-month Secondary Outcome Visit, including participants who  
804       had a Post-failure Secondary Outcome Visit earlier in the study. The 38-month Secondary  
805       Outcome Visits will occur at one of the following times:

- 806       • 2 months ( $\pm 4$  weeks) after the 36-month Primary Outcome Visit if:  
807            ○ failure has not been met by 36 months, OR  
808            ○ failure is met at 36 months and does not require confirmation  
809       • 2 months ( $\pm 4$  weeks) after the Failure Confirmation Visit (40 months) following  
810        failure which requires confirmation at the 36-month Primary Outcome Visit  
811       • At 38 months ( $\pm 4$  weeks) after randomization if failure was confirmed prior to 36  
812        months

813     At the 38-month Secondary Outcome Visit, most participants will be wearing HOME spectacles  
814       that will be bifocals; however, some participants who have previously met failure criteria may  
815       not be wearing BFLs. A cover/uncover test at near will be performed for participants who are not  
816       wearing BFLs to determine whether they have esotropia (see test procedure #5); if esotropia is  
817       present, then +3.00D lenses will be required for near testing (except for the second Randot  
818       Preschool Stereotest measure, which is performed through the distance correction only). If any  
819       participant presents to the visit without their HOME spectacles (if prescribed) or if the spectacles  
820       do not meet the spectacle tolerance criteria as determined by lensometry, trial frames will be  
821       used for testing.

822     The following test procedures are to be performed in the order specified below; procedures 4-9  
823       must be performed by an examiner masked to original treatment assignment:

- 824       1. Lensometry (HOME spectacles)
- 825       2. Diplopia Assessment: Assess diplopia presence and frequency over the last week, by  
826        parental report. If present, classify diplopia frequency as “2 times or less per day” or  
827        “more than 2 times per day.”
- 828       3. Monocular VA Testing: through TOP of HOME spectacles (if wearing)

829     Items 4-10 will be performed by an examiner masked to original treatment assignment (SVLs or  
830       BFLs); most participants are measured in a BFL lens correction at this visit (unless previously  
831       released to treatment at investigator discretion).

- 832       4. Distance Randot Stereotest: through TOP of HOME spectacles (if wearing) at 3 m  
833        (masked)
- 834       5. Cover/uncover test at near (for participants NOT currently wearing BFLs) to determine  
835        the optical correction to be used for Randot Preschool Stereoacuity #1, Randot Butterfly,  
836        Worth 4-Shape, and ocular alignment at near (cover/uncover, SPCT, and PACT testing)  
837        (tests #6, 7, 8 and 10 below):

- 838     • Perform a cover/uncover test at near through the HOME spectacles (or without  
839       spectacles, if none were prescribed)
- 840     • If an esotropia is present on the cover/uncover test at near, the specified testing must  
841       be completed in either 1) +3.00 lenses placed in Halberg or Janelli clips attached to  
842       the HOME spectacles or 2) a trial frame with a lens power that is +3.00D more than  
843       the HOME spectacles.
- 844     • If no esotropia is present on the cover/uncover test at near, the specified testing must  
845       be completed through the HOME spectacles (or without spectacles, if none were  
846       prescribed).
- 847     6. Randot Preschool Stereoacuity Test #1: through BOTTOM of HOME spectacles if  
848       currently wearing BFLs (otherwise, see step #5) at 33 cm\* **(masked)**
- 849     7. Random Dot Stereo Butterfly test: through BOTTOM of HOME spectacles if currently  
850       wearing BFLs; (otherwise, see step #5) at 33 cm\* **(masked)**
- 851     8. Preschool Worth 4-Shape test: through BOTTOM of HOME spectacles if currently  
852       wearing BFLs (otherwise, see step #5) at 33 cm\* **(masked)**.
- 853     9. Randot Preschool Stereoacuity Test #2: through TOP of HOME spectacles for at 33 cm\*  
854       **(masked)**
- 855     10. Ocular Alignment Testing: in HOME spectacles **(masked)**
- 856       • Cover/uncover test, SPCT, and PACT at 3 m through TOP of HOME spectacles
- 857       • Cover/uncover test, SPCT, and PACT through BOTTOM of HOME spectacles if  
858        currently wearing BFLs (otherwise, see step #5)

859     \*Test distance for near stereoacuity/binocular testing is 33 cm rather than 40 cm because of  
860       the focal length of the +3.00 D add.

861     Study follow-up will end for all participants after the 38-month Secondary Outcome Visit is  
862       completed.

### 863     **3.9 Inability to Complete a Study Visit**

864     If a child is not sufficiently cooperative (for any reason) for valid study data to be collected at a  
865       study visit, the child may return for continuation of the study visit on another day. This visit  
866       should be scheduled within 10 days or before the end of the study-visit window, whichever is  
867       sooner. The decision to have the child return on a subsequent day must be made by the masked  
868       examiner prior to the end of the masked exam. Any test procedures or measurements in question  
869       because of participant fatigue will be repeated at the return visit (all testing does not need to be  
870       repeated).

871     If the participant's family does not have sufficient time to complete a study visit and must leave  
872       prior to completing all required study testing (e.g., not able to stay for a cycloplegic refraction  
873       when meeting failure criteria), the participant must be brought back to complete testing within 10  
874       days or before the end of the study-visit window, whichever is sooner.

### 875     **3.10 Initiating Non-randomized Treatment for Esotropia (ET)**

876     Non-randomized treatment for ET is NOT permitted during the study unless the following 3  
877       conditions have been met:

- 878       1. Participant has met failure criteria (section 3.5)

- 879        2. Failure was confirmed either at the initial visit (section 3.5) or at the Failure  
880        Confirmation Visit (section 3.6)  
881        3. Participant has completed their Post-failure Secondary Outcome Visit (section 3.7).

882        If none of the failure criteria are met but the participant is experiencing overwhelming social  
883        concerns or significant symptoms (*other than frequent or constant diplopia at distance or near,*  
884        *which is a failure criterion*) associated specifically with the ET, the investigator **must call one of**  
885        **the Protocol Chairs** to discuss the case and obtain approval for an exception prior to initiating  
886        any non-randomized treatment for ET.

887        To the extent possible, participants for whom non-study treatment is planned (after discussion  
888        with Protocol Chair) should proceed as if one of the three protocol-specified failure criteria were  
889        met. Thus, they should complete the additional testing in section 3.5.1 (including the cycloplegic  
890        refraction) and a Post-failure Secondary Outcome Visit (section 3.7) prior to initiating any non-  
891        study treatment. The SVL participants will be prescribed BFL spectacles to be worn prior to the  
892        Post-failure Secondary Outcome Visit and the BFL participants should continue wearing BFLs.

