### 619 **3.5 Failure Criteria**

620 Treatment failure is defined as meeting one or more of the following criteria at any follow-up  
621 visit between 3 months to 36 months inclusive:

- 622 1. Constant ET  $\geq 15\Delta$  by SPCT at distance. (NOTE: intermittent ET and esophoria of any  
623 magnitude are NOT considered failures).
- 624 2. Decrease in near stereoacuity on the Randot Preschool Stereoacuity Test (at 33 cm) of 2  
625 or more levels from baseline (see levels below) stereo or from 960" (equivalent to 800"  
626 when measured at 40 cm) at baseline to nil (*criteria not applicable if nil near stereo at*  
627 *baseline*)
  - 628 • Baseline stereoacuity is defined as the near stereoacuity performed with +3.00 D  
629 added to the participant's enrollment distance spectacle correction in trial frames.
  - 630 • At all follow-up visits, the best of two stereo measures in the OFFICE lenses will be  
631 used to determine treatment failure.
  - 632 • Stereoacuity values are calculated for the 33 cm test distance required for testing  
633 through the added +3.00 D lenses at near (instead of the standard 40 cm). **NOTE:**  
634 Participants without measurable near stereoacuity at baseline cannot fail by  
635 stereoacuity criteria.

636  
637  
638**Table 2. Baseline and Follow-up Randot Preschool Stereoacuity Test Levels for Defining Treatment Failure**

Baseline Stereoacuity (in trial frames with lens power that is +3.00D more than distance correction) a	Follow-up Stereoacuity for Treatment Failure (best of two tests in OFFICE spectacles)
48" (40" at 40 cm)	120" or worse
72" (60" at 40 cm)	240" or worse
120" (100" at 40 cm)	480" or worse
240" (200" at 40 cm)	960" or worse
480" (400" at 40 cm)	Nil
960" (800" at 40 cm)	Nil
Nil	Not applicable

639  
640  
641  
642  
643  
644  
645  
646  
647  
648  
649  
650  
651  
652  
653  
654  
655  
656  
657  
658  
659  
660  
661  
662  
663  
664  
665  
666  
667  
The two sphere powers should be added and a single lens used for the spherical power component of the trial frames.

3. Binocular diplopia with a frequency of “more than 2 times per day” over the last week by parental report.
4. If any nonsurgical or surgical treatment for ET other than the randomized treatment is started before the participant meets failure criteria, the participant will be considered a failure at the visit at which the non-randomized treatment is prescribed.

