## 1198 **7.6 Analysis of Primary Outcome – Treatment Failure by 36 Months**

1199 There may be participants who are lost to follow-up before their 36-month primary outcome data  
1200 are collected. To use the data collected from these participants before they are lost to follow-up,  
1201 a time-to-event analysis will be performed for the primary outcome. For participants who meet  
1202 failure criteria before or at the 36-month Primary Outcome Visit, time to treatment failure will be  
1203 defined as the time from randomization to the visit at which the failure is confirmed (either at the  
1204 initial visit or later at a Failure Confirmation Visit because the spectacle correction must be  
1205 updated [section 3.6]). If a participant is prescribed non-randomized treatment for ET before  
1206 meeting failure criteria, they will be considered a failure at the time when such treatment is  
1207 prescribed. Participants lost to follow-up are considered censored at the time of their last  
1208 recorded visit. If a participant is lost to follow-up before failure is confirmed, they will be  
1209 censored at their last visit for the primary analysis.

1210 The hazard ratio of treatment failure for treatment with BFLs versus SVLs and a two-sided 95%  
1211 confidence interval (CI) will be estimated with a Cox proportional hazards model. The model  
1212 will be adjusted for baseline near stereoacuity by the Randot Preschool Stereotest (RPS) in +3.00  
1213 D trial frames and baseline magnitude of the distance esodeviation by SPCT. The treatment  
1214 group difference in the probability of failure and a two-sided 95% CI will be estimated using the  
1215 direct adjustment method. The proportional hazards and functional form assumptions will be  
1216 evaluated.

1217 The timing and composition of failures (distance motor, near stereoacuity, diplopia, starting non-  
1218 protocol treatment) will be tabulated by treatment group to aid in the interpretation of the  
1219 treatment group difference for failure probability by 36 months.

1220 **7.6.1 Sensitivity Analyses for Primary Outcome**

1221 As a sensitivity analysis, if a participant meets the failure criteria prior to a required spectacle  
1222 update but is lost to follow-up before the failure is confirmed, the participant will be treated as a  
1223 failure at the time when they initially met the failure criteria (suspected failure). The primary  

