1224 analysis will be repeated with these unconfirmed failures being counted as failures.

1225 As an additional sensitivity analysis, treatment crossovers (BFL group participants who have  
1226 bifocals formally discontinued and begin to wear SVL; SVL group participants prescribed  
1227 bifocals) that occur before meeting any of the clinical measures for failure will be censored at the  
1228 visit date when treatment crossover occurred.

1229 **7.6.2 Contingency Plan for Primary Outcome**

1230 If the assumptions for the Cox model are not satisfied, an exact logistic regression model with  
1231 the same covariates will be attempted. If the adjusted model fails to converge, a model will be fit  
1232 without the adjustment for covariates. If the exact logistic regression still fails to converge,  
1233 Barnard's exact test will be performed.

1234 **7.7 Analysis of Secondary Outcomes**1235 **7.7.1 Binocular Function Test Score in BFLs at the Secondary Outcome Visit**

1236 A secondary outcome is the binocular function test score at the Secondary Outcome Visit (Post-  
1237 failure Secondary Outcome visit if failed or 38-month Secondary Outcome Visit if not failed).  
1238 The test score is assigned on an ordinal scale that combines the results of the RPS test, Random  
1239 Dot Stereo Butterfly test, and Preschool Worth 4-shape (W4S) test that were measured using the  
1240 bottom portion of the participants' BFLs. Given that BFLs can potentially reduce the magnitude  
1241 of near ET, which might in turn improve near stereoacuity, it was felt critical to measure  
1242 binocular function after a period of BFL wear in both treatment groups. Consequently, after 36  
1243 months of SVL or BFL wear, the SVL group will be prescribed BFLs, the BFL group will  
1244 continue wearing their BFLs, and both groups will be re-assessed at the 38-month Secondary  
1245 Outcome Visit. Because participants who meet failure criteria for the primary outcome at a prior  
1246 visit must be released to treatment at investigator discretion, these participants will be prescribed  
1247 BFLs (if in the SVL group) or continue in BFL (if in the BFL group) and return within 2 months  
1248 after meeting failure criteria for a Post-failure Secondary Outcome Visit.

1249 The possible levels of binocular function will be 48, 72, 120, 240, 480, 960 arcsec (RPS test),  
1250 2400 arcsec (Random Dot Stereo Butterfly test), and 10,000 or 100,000 arcsec (fusion or  

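### Read literally, failure criterion 4 scores children on the section 3.10 exception pathway differently in the two arms, and section 3.10 does not say which failure status or date applies

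*Protocol*

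**What the plan says.** Criterion 4 in Protocol section 3.5 covers surgical or nonsurgical treatment for esotropia, other than the randomized treatment, that is started before a failure criterion is met. In that case "the participant will be considered a failure at the visit at which the non-randomized treatment is prescribed". Section 7.2 repeats the rule, and so does the primary analysis in section 7.6: "they will be considered a failure at the time when such treatment is" prescribed.

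Section 3.10 deals with a child in either arm who meets no failure criterion but has severe social difficulty or symptoms from the esotropia. With a Protocol Chair's approval, non-study treatment may be planned. As far as possible the child is first handled as though one of the three clinical criteria had been reached. That means the additional testing of section 3.5.1 and a Post-failure visit, both before any non-study treatment begins. For the interval, "The SVL participants will be prescribed BFL spectacles to be worn prior to the" "Post-failure Secondary Outcome Visit and the BFL participants should continue wearing BFLs".

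The second sensitivity analysis in section 7.6.1 names two crossovers: BFL children whose bifocals are formally stopped in favour of SVLs, and SVL children prescribed "bifocals) that occur before meeting any of the clinical measures for failure will be censored at the" visit at which the crossover took place.

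**The concern.** Bifocals are the randomized lens in one arm and a non-randomized esotropia treatment in the other. The step that section 3.10 requires of every child on the pathway therefore meets criterion 4 in the SVL arm and not in the BFL arm. The BFL child becomes a failure only through a later prescription. That may come after the Post-failure visit or after 36 months, or it may never come if the plan is dropped.

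This component of the primary composite would then be ascertained differently by arm. The treating investigator who starts the process is unmasked (section 3.2). In the primary analysis the difference adds or advances failures in SVL relative to BFL. In the 7.6.1 crossover analysis it runs the other way, so for these children that analysis does not test the primary result cleanly.

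**Working it through.** **Two identical courses, scored by the literal text**

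| Course after approval | Arm | Primary analysis (3.5, 7.6) | Crossover analysis (7.6.1) |
|---|---|---|---|
| About 2 months in BFLs, then no other treatment | SVL | Failure when BFLs are prescribed | Censored then |
| | BFL | Not a failure | Not a failure |
| About 2 months in BFLs, then a treatment other than SVLs, such as surgery | SVL | Failure when BFLs are prescribed | Censored then |
| | BFL | Failure when that treatment is prescribed | Still a failure |

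Section 7.6.1 supports the literal reading. Censoring SVL children given bifocals before any clinical failure measure would be largely needless if the primary analysis did not count them.

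**The plan's own figure.** Inputs from section 7.3: 5% SVL, 15% BFL, two-sided 5%, 90% power.

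n per arm = [1.960·√(2·0.10·0.90) + 1.282·√(0.05·0.95 + 0.15·0.85)]² / 0.10² ≈ 187.1, so 188 per arm and 376 in total. Then 188/0.85 gives 222 per arm and 444 in total. Both reproduce; the sample size is not in question.

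**Uncounted events.** The protocol gives no frequency, so these are assumptions. Let x be the share per arm failing only through section 3.10 (taken as equal in both arms), and f the share of BFL entrants never scored. Of 222 per arm, 1% to 5% is 2 to 11 children. The compared rates are 5% + x (SVL) and 15% + x(1 − f) (BFL), so the difference is 10 points − x·f. At 188 per arm:

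| x | Power, f = 0 (equal counting) | f = 0.5 | f = 1 |
|---|---|---|---|
| 1% | 87.6% | 84.7% | 81.5% |
| 2% | 85.0% | 78.3% | 70.0% |
| 3% | 82.5% | 71.2% | 56.7% |
| 5% | 77.7% | 56.1% | 31.0% |

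The f = 0 column lies below 90% only because both rates rise while the difference stays at 10 points. The effect of unequal counting is read across each row.

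With no true difference (10% clinical failure in each arm), rejection at the nominal 5% level for f = 0.5 and f = 1 is:
- x = 1%: 5.3% and 6.2%
- x = 2%: 6.1% and 9.5%
- x = 5%: 10.8% and 31.0%

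**Delay alone.** Every BFL entrant is still scored, only later, in a simulation with exponential times, 10% clinical failure per arm and a cut at day 1096. A 60-day shift gives a BFL/SVL rate ratio of about 0.99 (x = 2%) or 0.98 (x = 5%). A 258-day shift gives 0.96 or 0.92. These include the few events pushed past the cut.

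**Late entry.** The latest allowable 30-month visit is day 1004, and the Post-failure target window ends 88 days later: 1004 + 88 = 1092, just inside the 36-month target day of 1096. At the outer allowable limit, even an on-target 30-month entry gives 913 + 258 = 1171. That is past the target day, though within the 36-month visit's allowable window (to day 1278).

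**Primary against 7.6.1.** In simple proportions, 7.6.1 compares about 5% with 15% + x(1 − f), a difference of 10 points + x(1 − f). With x = 2% and f = 0.5 the primary difference is 9 points and the 7.6.1 difference 11. The 2-point gap comes from scoring alone.

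**The case against.** A reader might infer that the protocol lays down a rule under which an SVL child fails that day and a BFL child about two months later or never. It does not. Handling the child as though a clinical criterion had been met, with the 3.5.1 testing and a visit named Post-failure, can be read as failing both arms at the same visit. A second neutral reading also exists: section 3.10 places the SVL child's bifocals before any non-study treatment, so criterion 4 might be meant to wait for the later treatment in both arms. Both readings stand as possibilities. Neither is stated, and the as-though instruction is spelled out only as procedures, with no failure status or date.

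Other limits also stand:
- Failure at once in the SVL arm assumes spectacles within tolerance. Otherwise section 3.5.1, if followed, first updates the randomized lens and requires a Failure Confirmation Visit.
- Criterion 4 is triggered by treatment started but dated to its prescription, so a BFL child's later treatment, if ordered at the exception visit, could be dated to that visit.
- The 30-to-258-day window counts from confirmed failure and is the outer limit; the plan is 2 months (4 to 12 weeks). It is not a stated delay to scoring.
- Entry needs Protocol Chair approval. Sections 7.6 and 7.11 tabulate failure composition and non-study treatment by arm, so an imbalance would be partly visible.

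It can also be said that two analyses leaning opposite ways bracket the answer. In the simple calculation they do, so 7.6.1 does not make the result uninterpretable. But a gap between the two would not show whether treatment or scoring produced it.

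**Conclusion.** The point holds as a conflict between passages. Criterion 4 applied literally scores 3.10 entrants differently by arm, section 3.10 hints at equal handling without fixing it, and 7.6.1 is unequal in the other direction. This is more than missing detail that an analysis plan might supply, because the protocol's own rule for a primary-endpoint component gives arm-dependent ascertainment.

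The documents do not support the claim that the primary analysis is materially biased against SVL. That would need an entry rate and a share of BFL entrants never scored, and neither is given. The numbers are probably small. At x = 1% and f = 0.5 the power loss is about 3 points (87.6% to 84.7%); it becomes serious only if several percent enter and many BFL exceptions are never followed by another treatment. Unequal counting is the issue; a two-month delay alone is close to negligible. The correction is worth making because it is cheap and concerns the primary endpoint.

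**What to change.** Reconcile sections 3.5, 3.10, 7.2, 7.6 and 7.6.1 so that 3.10 entrants in both arms are scored as the same event on the same date. One rule that fits the existing as-though wording is to count a child in either arm as a failure at the study visit at which the 3.10 pathway begins, whatever lens is worn in the following two months. State how this works when spectacles are out of tolerance at that visit. Record the visit on the case report form: section 3.10 requires a call and approval but does not say that the date is captured. In 7.6.1, handle 3.10 entrants identically in both arms, either censoring both at that visit or counting both.

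The cost is a few sentences and one data field, settled before outcomes are compared by arm. The downside is that a few BFL children who never start another treatment would count as failures, as their SVL counterparts already do under the literal text. That widens criterion 4 slightly beyond treatment actually started, and the protocol should say so. Treatment is unchanged.
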